5.2.2. Analysis of subject disposition

5.2.2.1. Subject disposition

Frequency counts and percentages for all the following variables will be presented in a summary table by core treatment group and overall based on the FAS:

Core study:

- Subjects randomized in the core study;
- Subjects treated in the core study;
- Subjects prematurely discontinued treatment in the core study;

- Subjects completed treatment in the core study;
- Subjects prematurely discontinued from the core study;
- Subjects completed the core study per protocol;
- Subjects completed the core treatment and study per protocol;
- Subjects completed the core treatment and study as protocol and did not enroll in the extension study.

Extension study:

- Subjects enrolled in the extension study;
- Subjects treated in the extension study;
- Subjects prematurely discontinued treatment in the extension study;
- Subjects interrupted treatment for planned pregnancy;
- Subjects completed treatment in extension study (further split into: "Completed as per protocol" or "Approved Drug Available For Indication");
- Subjects prematurely discontinued from the extension study;
- Subjects completed the extension study;
- Subjects completed the extension treatment and study per protocol;
- Subjects prematurely discontinued from treatment or study in the extension study.

The denominator for percentages for core study variables above will be based on the number of randomized subjects in the core study. The denominator for percentages for the extension study variables above will be based on the number of enrolled subjects in the extension study (except for the percentage of 'enrolled in the extension study', which will be based on the number of randomized subjects in the core study).

A subject disposition flow-chart will be produced including all the disposition information listed above.

The number and percent of subjects in the EXTS are summarized by country and site, by core study treatment group, and overall.

All subject disposition variables will be presented in a dedicated listing.

5.2.2.2. Study treatment and study discontinuation

Frequency counts and percentages for all subjects who discontinued treatment, all subjects who discontinued study, reasons for discontinuation of treatment, and reasons for discontinuation of study, will be presented in a summary table which will be stratified by core study treatment and overall, for the Extension Analysis Period using the EXTS.

A KM plot for time to premature treatment discontinuation will be produced for the Extension Analysis Period on the EXTS. Subjects that complete the study treatment will be censored at the date of study treatment completion.

Reasons for treatment discontinuation in the extension and reasons for extension study discontinuation will be presented in separate listings.

5.2.3. Analysis sets

The number and percentage of subjects in each analysis set are summarized in a table, by core treatment group, and overall. Percentages are based on the FAS.

A listing of subject membership in the different analysis sets will be created.

5.2.4. Time in study

Time in study will be analyzed, by core treatment group and overall, separately for each of the following Analysis Periods:

- Extension Analysis Period (using EXTS);
- Combined Analysis Period (using EXTS).

Time on study will be summarized descriptively, separately for Combined and Extension Analysis Period as follows:

- Time in study (months): descriptive statistics;
- Time in study (months) by category (cumulative): frequency counts and percentages.

A KM plot for time to end of extension study will be produced for the Extension Analysis Period on the EXTS. Subjects complete study will be censored at the date of study completion.

Time on study information will be included in subject disposition listing(s).

5.3. Analysis of efficacy variables

5.3.1. Definition of Endpoint(s)

5.3.1.1. Relapse-related variables

5.3.1.1.1. Annualized Relapse Rate (ARR)

The ARR is defined as the number of relapses per subject-year.

The ARR will be calculated for both confirmed relapses and for all relapses, for both the Combined and the Extension Analysis Periods.

To evaluate the ARR for both the Combined and the Extension Analysis Periods, the following variables will be derived per subject and Analysis Period:

- Number of all relapses (confirmed and unconfirmed) from start date of the Analysis Period up to the end of Analysis Period;
- Number of confirmed relapses from start date of the Analysis Period up to end of analysis;
- Length of observation expressed in years, defined as: (Analysis Period end date Analysis Period start date of + 1) in days, divided by 365.25.
- Logarithm of the length of observation during Analysis Period as derived above.

Additionally, for the Core Analysis Period, the following ARR related variables from the core study will be included in the ADaM dataset as derived in the core study:

- Number of confirmed relapses from date of randomization in the core up to core EOS;
- Length of observation during the core study expressed in years, defined as: [core EOS date date of randomization in the core + 1] in days, divided by 365.25;

Additionally, the number of confirmed relapses and length of observation time will be derived per 24-week time period, separately for the Core and the Extension Analysis Periods, for the following time periods:

Core Analysis Period

- Core Week 0-24: \geq Core Day $1 \leq$ Core Day 168;
- Core Week 24-48: > Core Day 168 ≤ Core Day 336;
- Core Week 48-72: > Core Day 336 ≤ Core Day 504;
- Core Week 72-96: > Core Day 504 ≤ Core Day 672;
- Core Week 96-EOS: > Core Day 672 ≤ Core EOS;

Extension Analysis Period

- Extension Week 0-24: ≥ Extension Day 1 ≤ Extension Day 168;
- Extension Week 24-48: > Extension Day 168 ≤ Extension Day 336;
- Extension Week 48-72: > Extension Day 336 ≤ Extension Day 504;
- Extension Week 72-96: > Extension Day 504 ≤ Extension Day 672;

•

- Extension Week 96-120: > Extension Day 672 ≤ Extension Day 840;
- Extension Week 120-144: > Extension Day 840 ≤ Extension Day 1008;
- Extension Week 144-168: > Extension Day 1008 ≤ Extension Day 1176;

_

- Extension Week 168-192: > Extension Day 1176 ≤ Extension Day 1344;
- Extension Week 192-216: > Extension Day 1344 ≤ Extension Day 1512;
- Extension Week 216-Extension EOS: > Extension Day 1512 ≤ Extension EOS;

Core Day 1 is the date of randomization in the core study. Extension Day 1 is the date of first ponesimod administration in the extension study. In the event that a subject has their core EOS visit date recorded after their extension treatment start date, the extension treatment start date will be considered to be Extension Day 1 and the core EOS will be considered to be the extension treatment start date minus 1 day.

For both the core and extension studies, the number of relapses is derived according to the number of relapses entered on the eCRF module 'Relapse Summary'. Whether a relapse is confirmed is according to the treating neurologist / principal investigator, i.e., according to the question 'Relapse meeting the criteria for a confirmed relapse?' on eCRF module 'Relapse Summary'.

Also based on the eCRF module 'Relapse Summary', each reported relapse episode is assessed as being treated with corticosteroids (as per eCRF question 'Treatment of relapse with corticosteroids?') and as leading to hospitalization (as per eCRF question 'Did the MS relapse require hospitalization for reasons other than administration of IV corticosteroids?'). These relapse

qualifiers are solely derived from eCRF module 'Relapse Summary', i.e., irrespective of corresponding documentation in eCRF module 'Corticosteroids for Treatment of Relapse'.

5.3.1.1.2. Time to first (confirmed) relapse

The time to first (confirmed) relapse is defined as:

Date of first (confirmed) relapse (in either the core or extension study) minus date of randomization in the core study + 1 in days.

Time to first (confirmed) relapse is calculated over the Combined Analysis Period only. The following censoring rules are applied:

- Subjects who entered the extension study and remained free of relapses will be censored at the extension EOS date;
- Subjects who prematurely discontinued from extension study and remained free of relapses will be censored at the date of last contact.
- Subjects who did not enter the extension and ended the core study free of relapses will be censored at the core study EOS date;
- Subjects who prematurely discontinued from core study and remained free of relapses will be censored at the date of last contact.

For censored subjects, the time is defined as EOS – date of randomization + 1 in days.

5.3.1.1.3. Duration of (confirmed) relapse

Duration of (confirmed) relapse (days) is derived as (confirmed) relapse end date – relapse start date + 1 day. Duration of (confirmed) relapse will be set to be missing if either start date or end date is missing or incomplete.

5.3.1.2. MRI-related variables

MRI data are read centrally by Medical Image Analysis Center (MIAC) and provided to the sponsor. The derivation of the MRI endpoints is according to the visit identification in the MIAC database.

In the core study, MRI scans are scheduled at Baseline, at the Week 60 Visit, and the Week 108 (EOT) Visit. For subjects prematurely discontinuing treatment, an additional premature EOT visit MRI is scheduled. In addition, unscheduled MRI scans may be conducted any time. MRI scans are used as mapped in the core study, as described in the core study SAP.

In the extension study, MRI scans are scheduled at Week 48, Week 96, Week 144, and Week 192 Visits, and at the Week 240 EOT (for Ukraine subjects in addition at Week 288 EOT) Visit. In addition, unscheduled MRI scans may be conducted any time including at planned pregnancy interruption and re-initiation visits.

MRI variables are based on the result from the corresponding nominal visit (or from a re-mapped premature EOT or pre-planned pregnancy visit.

5.3.1.2.1. T1 Gd+ lesions

The following variables are derived at each scheduled visit during the Combined Analysis Period:

- Total number of T1 Gd+ lesions, derived as:
 Number of new T1 Gd+ lesions (T1GdNewR) + number of persisting T1 Gd+ lesions (T1GdR);
- Total number of T1 Gd+ lesions, categorized (0, 1, 2, 3, 4, 5, 6-10, 11+).

In addition, the following analyses will be conducted:

- The cumulative number of Gd+ T1 lesions from core baseline to extension EOS and corresponding number of scans included will be used as derived.
- Absence of Gd+ T1 lesions at each visit: 'Gd+ T1 lesions at each visit' are considered 'absent', if the number of Gd+ T1 lesions at each visit is zero. If > 0 they are considered 'present'. This applies to nominal visit collected in the CRF.
- Absence of Gd+ T1 lesions from Core baseline until extension EOS: Absence of new Gd+ T1 lesions from Core baseline to extension EOT (including all unscheduled scans) is defined 'absent' if the 'number of new Gd+ T1 lesions' at all post-baseline MRI scans up to the extension EOS is zero. This includes all scheduled and all unscheduled visits. If > 0 at any visit it is considered 'present'. The corresponding 'Number of MRI scans' and time to last MRI scan are derived. If no MRI result at the visit is available (based on visit window), the information is considered missing (for lesion free subjects).
- Total volume of T1 hypointense lesions and the change from baseline: Total volume of T1 hypointense lesions (mm3) (variable T1BHVOL) is recorded by the central reader at each visit. The change from Core baseline is derived as the change from total volume of T1 hypointense lesions at Core study Visit 2-Baseline. The change from Extension baseline is derived as the change from last available record of total of T1 hypointense lesions prior to Extension Baseline.
- Proportion of Gd+ T1 lesions at Core Baseline evolving to persistent black holes (PBHs): It is the proportion (%) of 'Number of T1 hypointense lesions (persistent black holes) evolved from T1 Gad.-enhancing lesion at V2 Baseline core study' (variable T1BHV2C) at each scan visit out of the 'Number of Gd+ T1 lesions at Core baseline'.

Note: Gd+T1 lesions are assumed to not enhance for more than 12 weeks. This requires handling of data as follows:

- If at a visit, number of persisting T1 Gd+ lesions are not recorded, the number of Gd+T1 lesions is the number of new T1 Gd+ lesions. Rationale: As per central reader processes persisting T1 Gd+ lesions are not assessed for subjects with scheduled MRIs scheduled more than 12 weeks apart.
- If at an MRI scan which is >12 weeks (84 days) since the last previous scheduled MRI scan a persisting lesion count > 0 is recorded, these persisting lesions are considered implausible and therefore not to be considered in derivations of total Gd+ T1 counts.

5.3.1.2.2. New or enlarging T2 lesions

The following variables will be evaluated at each visit:

- Total number of new or enlarging T2 lesions (relative to previous visit), derived as: Number of new or enlarging T2 lesions without gadolinium-enhancement (T2new_R) + new or enlarging T2 lesions with gadolinium-enhancement (T2newGd R);
- Total number of new or enlarging T2 lesions (relative to previous visit) categorized (0, 1–5, 6–10, 11+);
- Cumulative new or enlarging T2 lesions from core baseline up to each visit up to extension EOS. Cumulative new or enlarging T2 lesions will not be derived if any post-baseline record is missing with a reason of "Dependent evaluation missing: Reference required for evaluation is not available (missing or rejected)" in the SDTM variable MO.MOREASND.

Where "new" refers to last prior available scheduled visit (note: planned pregnancy visits are considered scheduled MRIs for analysis), and specifically for evaluations at extension study Visit 7, results are compared to Visit 14 EOT from the core study.

In addition, the follow cumulative variables are derived:

The cumulative number of new or enlarging T2 lesions from core baseline to extension EOS is derived as the sum of number of the sum of total number of new or enlarging T2 lesions (as derived above) at all post-baseline MRI at all post-core baseline MRI scans up to the extension EOT MRI visit. This includes premature EOT scans if available, and unscheduled scans only if it is the last available scan for the subject.

The time up to the last MRI (years) included in the above is derived as = Date of last MRI considered in derivation - core randomization date + 1 divided by 365.25 days.

Similarly, the cumulative number of new or enlarging T2 lesions from extension baseline to extension EOS is derived as described above, together with the time, where time is relative to enrollment in the extension study.

If the baseline MRI is missing, new or enlarging T2 lesions as compared to baseline cannot be assessed and consequently the endpoint is considered missing. The baseline MRI is considered missing if presence of T1 Gd+ lesions at baseline is missing. The following analyses will be conducted as well:

- **Absence of new or enlarging T2 lesions at each visit:** 'New or enlarging T2 lesions' are considered 'absent', if the number of New or enlarging T2 lesions at each visit is zero. If > 0 they are considered 'present'. This applies to nominal visit collected in the CRF.
- Absence of new or enlarging T2 lesions from Core baseline until extension EOS: Absence of new or enlarging T2 lesions from Core baseline to extension EOT (including all unscheduled scans) is defined 'absent' if the 'number of new or enlarging T2 lesions' at all post-baseline MRI scans up to the extension EOS is zero. This includes all scheduled and all unscheduled visits. If > 0 at any visit it is considered 'present'. The corresponding 'Number of MRI scans' and time to last MRI scan are derived. If no MRI result at the visit is available (based on visit window), the information is considered missing (for lesion free subjects).

Total volume of T2 lesions and the change from baseline: Total volume of T2 lesions (mm3) (variable T2VOL) is recorded by the central reader at each visit. The change from Core baseline is derived as the change from total volume of T2 lesions at Core study Visit 2-Baseline. The change from Extension baseline is derived as the change from last available record of total volume of T2 lesions prior to Extension Baseline.

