1.2.1. Core study follow up period and transition into the extension study

Eligible subjects may enter the extension study following the safety follow-up (FU) period of the core study. For subjects transitioning into the extension study, the core study safety FU period concludes with a safety Follow-up Visit 1 (FU1) or with an abbreviated Follow-up Visit 2 (FU2) at 14-22 and 23-37 days, respectively, after the last dose of the study drug in the core study (End of-Treatment; EOT). The abbreviated FU2 visit will take place only if the compliance with teriflunomide elimination procedure was deemed not sufficient by the investigator at FU1 visit but transition to the extension study is still planned. The core study FU period ends when all assessments of FU1 or FU2 (whichever applies) have been completed. At FU1 or FU2 (whichever applies) the subject's compliance with teriflunomide elimination procedure needs to be assessed as sufficient by the investigator in order to confirm eligibility for the extension study.

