5.1.9.1. Extension enrollment date

The extension enrollment date is the date when the subject signed the Informed Consent Form and is taken directly from RAVE.

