5.3.2.3.2. New or enlarging T2 lesions

The total number of new or enlarging T2 lesions per visit will be summarized descriptively as continuous and in categories (anticipated categories: 0, 1, 2, 3, 4, 5, 6-10, 11+), for the Combined Analysis Period on the EXTS.

The cumulative number of new or enlarging T2 lesions from core baseline up to extension EOS (Combined Analysis Period) (i.e. from baseline up to extension EOS) will be analyzed on the EXTS using a negative binomial regression model with core study treatment as a factor and the log of time up to last MRI (in years) considered for analysis as an offset variable. Mean model-based estimates and corresponding 95% CIs will be presented. The same model is applied for extension period on the EXTS.

Descriptive summary statistics for the cumulative number of new or enlarging T2 lesions from core baseline up to extension EOS on the EXTS will be presented by treatment group for continuous data and frequency per categories (anticipated: 0, 1–5, 6–10, 11-20, 20+), total counts and total cumulative observation time (time up to the last MRI scan in years) summed for all subjects, raw yearly rate (total count / total cumulative observation time). Descriptive summary statistics for the cumulative number of new or enlarging T2 lesions from extension baseline up to extension EOS on the EXTS will be presented in the same way.

Descriptive statistics on absence of new or enlarging T2 lesions by visit (frequency and percentages of subjects with lesions absent, present) will be presented by visit, and cumulative for absence of new or enlarging T2 lesions from Core baseline up to extension EOS will be tabulated. This analysis will be done for combined period using EXTS.

The total number of new or enlarging T2 lesions will be analyzed by visit for the Combined Analysis Period on the EXTS, using the negative binomial model, as described in Section 5.3.2.3.1, for the total number Gd+ T1 lesions per visit. The corresponding plots will also be presented.

Total volume of T2 lesions and change from baseline per visit is summarized descriptively based on observed data, for combine analysis period using the EXTS. Same analysis will be repeated using EXTS relative to Extension baseline during Extension period. The total volume of T2 lesion data will be listed using FAS.

T2 lesion data will be listed on the FAS.

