- 2) Visit 1 includes a pre-treatment period which lasts from signing of the informed consent until first dosing of study treatment. Ideally, all assessments and procedures of Visit 1 (e.g., signing of the informed consent, first study treatment dosing and post-dose cardiac monitoring) should occur on the same day as the core study FU1 or abbreviated FU2 (whichever applies). In all cases, informed consent should be signed no later than one day after FU1 or FU2 visit (whichever applies) and all assessments and procedures of Visit 1 must be completed (i.e., study treatment start) no longer than 7 days after signing of the informed consent. The date of Day 1 corresponds to the date of the first dose of study treatment in the extension study. The investigator should make every effort to minimize the duration between EOT of the core study and Day 1 of the extension study. Ideally the treatment interruption should last no longer than 15 days.
- 3) At every study visit, subjects are reminded to contact their principal investigator / treating neurologist at the clinical site immediately in the event of the appearance of any new or worsening neurological symptoms. In addition, the site will contact the subject 6 weeks (± 7 days) after each visit starting with Visit 4 (Week 12) in order to proactively inquire about any new or worsened neurological symptoms. Whenever, between visits, a subject experiences any new or worsening neurological symptoms, he/she must contact the principal investigator / treating neurologist, study nurse or clinical coordinator as soon as possible in order to complete a relapse assessment questionnaire [see protocol appendix 10].
- 4) Dermatological examination to be performed by a dermatologist.
- 5) Systolic / diastolic blood pressure: Only pre-dose except Day 1. On Day 1 pre-dose and hourly (± 15 min) for at least 4 hours post-dose and up to 12 hours.
- 6) ECGs: Only pre-dose except Day 1. On Day 1 pre-dose and hourly (± 15 min) for at least 4 hours post-dose and up to 12 hours.
- 7) OCT and/or ophthalmological examination to be performed at any visit in the presence of visual symptoms suggestive of macular edema or active uveitis.
- 8) PFTs including spirometry to be performed in all subjects; DL_{CO} to be performed in a subset of subjects at selected sites only.
- 9) Monitoring of hematology/chemistry every 4 weeks for the first 24 weeks after enrollment (±7 days).

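### Extension-period cumulative T2 lesions are counted from the core EOT scan but time is counted from extension consent, so the extension lesion rates are modestly overstated

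*SAP*

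**What the plan says.** **Start of the count.** SAP 5.3.1.2.2 reads each scan against the previous available scheduled one, and for the first scheduled extension MRI it is explicit: "specifically for evaluations at extension study Visit 7, results are compared to Visit 14 EOT from the core study". Section 5.3.1.2 and the visit schedule in 6.12 list no MRI at enrollment or Day 1. Sections 5.3.1.2.4 and 5.3.2.3.1 treat core EOT as the extension MRI baseline.

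**Start of the clock.** The same section says the extension count is paired with a time "where time is relative to enrollment in the extension study". Section 5.1.9.1 fixes that date: "The extension enrollment date is the date when the subject signed the Informed Consent Form". Under 1.2.1, FU1 and the abbreviated FU2 fall "at 14-22 and 23-37 days, respectively, after the last dose of the study drug in the core study", and FU2 takes place only if compliance with the elimination procedure was judged insufficient at FU1. The schedule notes in 6.12 allow consent up to one day after the follow-up visit.

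**Use.** Section 5.3.2.3.2 takes the log of time to last MRI as the negative binomial offset and then adds: "The same model is applied for extension period on the EXTS". It also asks for a raw yearly rate, total count over total time, presented in the same way for the extension. Premature EOT scans are included.

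**The concern.** A rate needs its events and its time to cover the same interval. Here the count opens at the core EOT scan and the clock opens at consent, after the core follow-up visit. Any T2 lesion that forms in between appears on the first extension MRI and enters the numerator, but the days in which it formed are left out of the denominator. The error goes one way, upward. It is a fixed number of days, so it weighs more on subjects with short extension follow-up, such as those who stop early or move to commercial supply. These rates are part of the MRI description of disease control in the extension, including after the switch from teriflunomide, and in a descriptive study the absolute rates are themselves results.

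**Working it through.** The SAP states no lesion rate, so there is no figure of its own to reproduce.

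**Inputs**
- FU1 at 14-22 days and FU2 at 23-37 days after the last core dose (1.2.1); consent 0-1 day later (6.12).
- Nominal Week 48 = Day 337, Week 96 = Day 673 and Week 240 = Day 1681 (5.1.10), each 7 × week + 1.
- 877 subjects enrolled (Section 3).
- Core EOT scan date relative to the last core dose: not in the SAP. Two assumptions are shown: scan on the day of the last dose, and scan 14 days later (the outer limit that 1.2.3.1 sets for the extension EOT visit, borrowed here).

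**Step 1: omitted days g, from core EOT scan to consent**
- Scan at last dose: FU1 14 to 22 + 1 = 23; FU2 23 to 37 + 1 = 38.
- Scan 14 days after last dose: FU1 0 to 9; FU2 9 to 24.

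**Step 2: overstatement per subject**
With consent on Day 1 and last scan on Day d, SAP time is d days (last MRI − enrollment + 1). Time from the reference scan, with the same + 1, is d + g. The overstatement is (d + g)/d − 1 = g/d.

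| Last scan | g = 14 | g = 23 (FU1 maximum) | g = 38 (FU2 maximum) | g = 24 (maximum, scan 14 days later) |
|---|---|---|---|---|
| Week 48, d = 337 | 4.2% | 6.8% | 11.3% | 7.1% |
| Week 96, d = 673 | 2.1% | 3.4% | 5.6% | 3.6% |
| Week 240, d = 1681 | 0.8% | 1.4% | 2.3% | 1.4% |

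Consent up to 7 days before Day 1 lengthens d slightly and barely changes these: 38/344 = 11.0%.

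**Step 3: pooled raw rate**
Assume exponential dropout with a share r reaching Week 240 and the last scan at leaving. Mean follow-up is 1681 × (1 − r)/(−ln r).
- r = 0.9: 1681 × 0.1/0.1054 ≈ 1595 days.
- r = 0.5: 1681 × 0.5/0.6931 ≈ 1213 days.

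The overstatement is g divided by mean follow-up: from 14/1595 = 0.9% to 38/1213 = 3.1% overall, and at most 23/1213 = 1.9% if all subjects go through FU1.

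**Step 4: pooled model rate**
The negative binomial model gives short follow-up relatively more weight, so its error is larger. A simulation of 877 subjects (assumed 1 lesion per year, dispersion 1.5, r from 0.5 to 0.9) compared the SAP offset with a scan-to-scan offset. For gaps of 13-38 days the model rate was 0.8-4.5% too high. For 13-22 days it was 0.8-2.6% too high. The simulation omits the + 1 from the scan-to-scan time, a difference of about 0.1 percentage point.

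**The case against.** The strongest case against is size. The reported quantities are a pooled rate and a model mean, not per-subject rates. With the simulation's rate and dispersion, an assumed 4 years of follow-up and about 438 per group, the standard error of a log rate is about √((1/4 + 1.5)/438) = 0.063. That is a 95% interval of roughly ±12%, much wider than the error. Section 2 makes every analysis exploratory, and the main efficacy focus is the Combined period (5.1.5.1, 6.2.1), which this clock does not touch. Starting time at randomization or enrollment is also the SAP's general convention for MRI variables. All of this stands and keeps the point minor. It does not make the two intervals match: the bias is systematic, and the SAP itself puts at least two weeks between the last core dose and consent.

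A reader might infer more than the SAP supports:
- *That every subject loses 2-5 weeks.* The upper part belongs to the exceptional FU2 route, and the whole range depends on an unstated scan date. With a later scan the lower bound is zero.
- *That the reported rate is off by about 11%.* That is the most exposed Week 48 case for one subject, not the pooled result.
- *That the comparison between core treatment groups is distorted.* Both groups follow the same gap rule, so the ratio is nearly unaffected unless FU2 use or time of leaving differs by group.
- *That an extension Day 1 MRI removes the gap.* Section 5.1.3.1 would accept one as baseline, but none is scheduled and 5.3.1.2.2 fixes the core EOT scan as the Visit 7 reference.

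**Conclusion.** The concern holds in modest form. As written, 5.3.1.2.2 opens the extension T2 count at the core EOT scan and its clock at consent, and no other section corrects this. The extension model rate and raw yearly rate are therefore biased upward. The likely pooled size is about 1-3% (raw) and 1-4.5% (model), resting on assumed dropout, lesion rate and dispersion and on a core EOT scan close to the last core dose. If that scan came later, the error shrinks and can vanish for some subjects. No conclusion of the trial is likely to turn on it. It merits a correction because it is a one-directional error in a reported result and actual scan dates remove it.

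**What to change.** - **T2, 5.3.1.2.2 and 5.3.2.3.2:** define extension time up to last MRI as (date of last MRI considered − date of the reference MRI actually used for the first extension read, i.e. the core EOT scan, + 1)/365.25. Use it for both the extension model offset and the raw yearly rate.
- **CUAL, 5.3.1.2.3:** apply the same definition. This section uses the same enrollment clock, so changing T2 alone would leave two denominators for the same scans.
- **CUAL analysis, 5.3.2.3.3:** reconcile. It gives an offset in years from core baseline and lists the extension-period analysis under it. Taken literally, that would make the denominator too long and the rate too low.
- **Footnote:** state that the interval, and the lesions counted in it, include the off-drug washout. The change aligns the denominator but does not turn the result into a purely on-ponesimod rate.

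The cost is a sentence in each section and one derivation from scan dates already held. Reported extension rates would fall by a few percent at most, and some off-drug time enters the denominator, which the footnote discloses.
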